9.1.4 Samples to be Assayed

Samples from subjects included in the PK dataset and who experience vomiting within the criteria for removal, as defined in the section 5.4 will be assayed.

9.2 Pharmacokinetic Parameters

The actual post-dose sample collection times will be used in the PK analysis.

The following PK parameters and observations will be calculated based on data from the PK population
[REDACTED]
later) for ba

- AUC_{0-t} : Area under the concentration-time curve from time zero until the last observed concentration, as calculated by the linear up/log down variant of the trapezoidal method.

- $AUC_{0-\infty}$: Area under the concentration-time curve from time zero to infinity (extrapolated)
- Residual area: Percentage of $AUC_{0-\infty}$ due to extrapolation from the time of the last observed concentration to infinity, calculated as $[1 - (AUC_{0-t}/AUC_{0-\infty})] \times 100$
- C_{\max} : Maximal observed concentration
- T_{\max} : Time when the maximal concentration is observed
- T_{lag} : Time of observation prior to the first observation with a measurable (non-zero) concentration.
- $T_{1/2 \text{ el}}$: Terminal elimination half-life
- K_{el} : Terminal elimination rate constant
- Cl/F : Apparent clearance
- V_z/F : Apparent volume of distribution
- R^2 : Coefficient of determination obtained from regression analysis

Additional PK parameters may be calculated. K_{el} , $T_{1/2 \text{ el}}$, and $AUC_{0-\infty}$ parameters will not be estimated for concentration-time profiles where the terminal linear phase is not clearly defined.

Sapropterin is an endogenous compound and therefore, should be analyzed both with and without baseline correction. Pharmacokinetic parameters will be calculated based on uncorrected plasma concentrations and baseline-corrected plasma concentrations, as appropriate. Baseline corrected for sapropterin will be performed by calculating the mean plasma pre-dose levels for each subject within each period of the study using the measured concentrations at the -1, -0.5, and the 0-hour time points. The mean of these pre-dose values will be the *baseline* for that period for that subject. The baseline value will be subtracted from all subsequent measured concentrations (including 0-hour) for the same subject within the same period. Negative baseline adjusted levels will be set to zero before the PK analysis. No adjustment of the pre-dose or post-dose concentrations will be performed for the baseline uncorrected data.

IRB Reviewed - June 12, 2024

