*Because λ_z could not be determined for some subjects due to insufficient concentration data in the terminal phase of the plasma curve, it was not possible to calculate $t_{1/2}$ and $AUC_{0-\infty}$ for these subjects. Thus, the number of subjects for the intact/fasting, dissolved/fasting, and intact/fed regimens in this comparison were 14, 17, and 18, respectively.

Based on the clinical pharmacology and biopharmaceutics review of Kuvan⁴, the pharmacokinetic parameters of sapropterin dihydrochloride 100 mg powder for oral solution are expected to be comparable to the 100 mg tablets based on their composition, solubility, and osmolarity. The powder formulation contains the same active ingredient in the same concentration, exhibits rapid dissolution using the dissolution method for sapropterin dihydrochloride tablets, has similar osmolarity in water, and its inactive ingredients are not expected to affect drug absorption and bioavailability.⁴ Absolute bioavailability or bioavailability for humans after oral administration is not known. In human plasma (*in vitro*), the protein-binding rate remained constant (22%–34%) within the concentration range of endogenous levels (approximately 3–10 ng/mL).²

Sapropterin is a synthetic form of BH4 and is expected to be metabolized and recycled by the same endogenous enzymes. *In vivo* endogenous BH4 is converted to quinoid dihydrobiopterin and is metabolized to dihydrobiopterin and biopterin. The enzymes dihydrofolate reductase and dihydropteridine reductase are responsible for the metabolism and recycling of BH4.^{1,2}

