8.5 Pharmacokinetic Assessments

8.5.1 Pharmacokinetic Blood Sample Collection and Processing

In each period, blood samples for PK analysis will be collected via an intravenous catheter or by direct venipuncture.

The PK Scientists will be contacted to evaluate the subject's continued participation in the study if any of the following incidents occur in any period:

- The 24-hour scheduled blood draw is missed; or
- At least two consecutively scheduled blood draws are missed.

The impact of these incidents on the estimation of PK parameters will be made as close to the time of occurrence as possible.

The planned volume of blood to be collected for this study, including that collected for eligibility and safety purposes, should not exceed 500 mL. Additional tests or blood draws could be performed, if deemed required by the Investigator or study staff.

Procedures for collection, processing, and shipping of PK blood samples will be detailed in a laboratory manual.

Plasma concentrations of the study treatment will be determined using a validated analytical method. Details of the analytical method will be provided in a separate document.

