8.8 Premature Termination of the Study

The study may be prematurely terminated by the Investigator following consultation with the Sponsor, by the Sponsor or by the regulatory authorities. Following a decision to discontinue the trial, the Investigator will promptly inform the active study subjects and the IEC responsible for this trial, stating the reasons for discontinuation of the study. It is the responsibility of the Sponsor (or representative) to report the premature termination of the study to the regulatory authority(ies), when required by the applicable regulatory requirement(s).

9. Statistical Analyses

For all PK analysis, all concentrations below the limit of quantification will be set to 0.

Samples with invalid concentration (due to bioanalytical or clinical issue) will be replaced by “0.00” when it occurs prior to dosing for PK parameters calculation. Otherwise, they will be set to missing for tabulation, graphical representation, and calculation purposes if it occurs after dosing.

The primary objective of this study is to evaluate the relative bioavailability of a new oral suspension formulation. Since this study is exploratory, no formal hypothesis testing is defined.

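### Tlag is defined for a drug absent before dosing; with endogenous sapropterin it is uninformative in uncorrected data and biased toward zero in corrected data when a true lag exists

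*Combined protocol and SAP*

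**What the plan says.** Section 9.2 lists Tlag among the PK parameters and defines it as "Time of observation prior to the first observation with a measurable (non-zero) concentration". It sets no threshold above baseline and gives no separate rule for either data set. The same section states: "Pharmacokinetic parameters will be calculated based on uncorrected plasma concentrations and baseline-corrected plasma concentrations, as appropriate". Section 9.3 plans descriptive statistics for both data sets.

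Three other provisions decide what counts as non-zero:

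- **Endogenous level.** Section 1.1 reports plasma protein binding "within the concentration range of endogenous levels", which it puts at about 3–10 ng/mL.
- **Uncorrected data.** Section 9.2: "No adjustment of the pre-dose or post-dose concentrations will be performed for the baseline uncorrected data". The opening of section 9 adds that "all concentrations below the limit of quantification will be set to 0". The limit itself is not given; section 8.5.1 says "Details of the analytical method will be provided in a separate document".
- **Corrected data.** The baseline is the mean of the -1, -0.5 and 0-hour values of that subject and period. It is subtracted from later values and from the 0-hour value itself. Then: "Negative baseline adjusted levels will be set to zero before the PK analysis".

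**The concern.** A first-non-zero rule finds the onset of absorption only if every sample before onset reads zero. Here that fails in two ways.

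In uncorrected data a quantifiable baseline makes the very first pre-dose sample non-zero. Tlag is then either zero by convention or undefined, because no sample precedes it.

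In corrected data only negative values become zero. A positive residual of any size, at 0 hours or later, ends the lag although no drug has been absorbed.

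The trial compares fed with fasting dosing, water with no water, and suspension with solution. Tlag is the listed parameter that addresses onset of absorption directly, so a table of small Tlag values in every treatment could be misread as evidence against a delay.

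**Working it through.** The plan states no Tlag figure, so there is none to reproduce.

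**Inputs from the documents:** the sampling grid (-1, -0.5, 0, 0.333, 0.667, 1, 1.5 h and later), the three-sample baseline, truncation of negatives at zero, endogenous levels of about 3–10 ng/mL, and mean Cmax of 63.0 to 105 ng/mL (Table 2).

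**Assumptions, not in the documents:** true lags of 0 to 1.1 h; lower limit of quantification (LLOQ) of 1 ng/mL, varied from 0.5 to 10; within-period baseline CV of 10–20%; independent normal noise of equal variance; a clear rise once absorption starts. If the first non-zero value is at 0 h, Tlag is taken as 0.

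**Step 1: uncorrected data.** With LLOQ 1 ng/mL and baseline 3–10 ng/mL, simulated Tlag is 0 in 100% of profiles for every lag. At a lag of 0.7 h and CV 10% this still holds for any LLOQ up to 2 ng/mL. The rule works only when the LLOQ exceeds the subject's own baseline, for example baseline 3 with LLOQ 5, or baseline 6 with LLOQ 8.

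**Step 2: corrected data.** Let m be the mean of the three pre-dose values and σ the noise SD.

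- The 0-hour residual is symmetric about zero, so P(positive) = 0.50.
- A drug-free post-dose residual has variance σ²(1 + 1/3). Two of them have covariance σ²/3, hence correlation (1/3)/(4/3) = 1/4.
- The 0-hour residual has covariance −σ²/3 + σ²/3 = 0 with each post-dose residual, so it multiplies the result by 1/2.

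Tlag is right only if every drug-free residual is ≤ 0. With k drug-free post-dose samples, counting post-dose samples only:

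- k = 1: 1/2 = 0.50
- k = 2: 1/4 + arcsin(1/4)/(2π) = 0.29
- k = 3: 1/8 + 3·arcsin(1/4)/(4π) = 0.185

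| True lag (h) | Correct grid value (h) | Right, 0-hour counted | Right, post-dose only |
|---|---|---|---|
| 0.35 | 0.333 | 25% | 50% |
| 0.7 | 0.667 | 14.5% | 29% |
| 1.1 | 1.0 | 9% | 19% |

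Simulation agrees. Only the sign of the noise matters, so baseline level and CV hardly change the table. At a lag of 1.1 h the mean reported Tlag is 0.16 h (about 0.32 h post-dose only). With no true lag, the reported 0 is right in 100% of profiles.

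**Step 3: the exclusion in section 9.1.3.** It drops periods whose corrected 0-hour value exceeds 5% of Cmax: 0.05 × 63.0 = 3.15 to 0.05 × 105 = 5.25 ng/mL. It removed no period in the runs with LLOQ 1 ng/mL.

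**Step 4: the other reading of the LLOQ rule.** If corrected values below the LLOQ also become 0, each residual need only stay below 1 ng/mL. For a lag of 0.667 h the right value is then returned in 99.6% (baseline 3, CV 10%), 85% (baseline 6, CV 10%) and 35% (baseline 10, CV 20%) of profiles.

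**Step 5: replacement rules.**

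- *Above the highest of the three pre-dose values, and still above it at the next sample.* By ranks, the last drug-free sample exceeds all three pre-dose values with probability 1/4, giving 75% right for k = 1 or 2. For k = 3 the first two samples may also both exceed them: 1/4 + 1/10 − 1/20 = 0.30, giving 70% right.
- *First corrected value above 5% of Cmax.* On the fed profile this was right in 97–100% of profiles for lags of 0 to 1.1 h.

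**The case against.** The strongest reply has four parts.

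1. **The uncorrected-data result needs a figure nobody can see here.** The LLOQ is in another document, and the 3–10 ng/mL range comes from a sentence on in vitro protein binding, not from pre-dose samples in this population. This stands as a condition. But an LLOQ above the baseline would leave the planned correction little to subtract, so the plan itself assumes a measurable baseline.

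2. **Tlag may be meant for corrected data only.** Section 9.2 allows parameters on either data set where appropriate, and the sentence introducing the list is partly redacted. That would settle the uncorrected half. It would not repair the rule for corrected data.

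3. **The LLOQ rule may cover corrected values.** Section 9 applies it to all PK analysis, and Tlag asks for a measurable concentration. On that reading the bias shrinks, sometimes almost to nothing (step 4). Section 9.2, however, mentions only negatives being set to zero, so the text leaves the point open.

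4. **Little depends on Tlag.** It is not a named primary endpoint and enters no visible model, ratio or confidence interval. Tmax has its own Wilcoxon test, and the concentration curves would show a delay. Tlag can also be recomputed later from the same concentrations. All of this stands and limits the importance.

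A reader might infer more: that Tlag would show no delay in any treatment whatever the truth, or that corrected Tlag is mostly noise. The documents do not support that. At a lag of 0.667 h about 25% of corrected profiles still give a non-zero Tlag (14.5% correct plus 10.5% at 0.333 h), and in these simulations a non-zero corrected value reflected a real delay. The fault is attenuation toward zero.

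**Conclusion.** The point holds, as a minor one. The Tlag rule does not fit an endogenous analyte. If the baseline is quantifiable, uncorrected Tlag carries no information on delay. In corrected data it is biased toward zero when a lag exists: right in about 9–25% of profiles for lags of about 0.33 to 1.1 h, about 19–50% if only post-dose samples count, and about 35–99.6% at 0.667 h if sub-LLOQ corrected values are zeroed with an LLOQ of 1 ng/mL. These ranges rest on the assumed lags, LLOQ, baseline CV and independent noise. When there is no lag the reported zero is correct. The AUC, Cmax and Tmax results do not depend on Tlag. The secondary endpoints are redacted, so whether Tlag is among them cannot be seen.

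**What to change.** Replace the Tlag line in section 9.2 with a rule of this kind: Tlag is reported for baseline-corrected data only and from post-dose samples only; it is the sampling time before the first post-dose concentration that clearly exceeds pre-dose noise and is still above it at the next sample.

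Fix the threshold before the concentrations are seen. Two candidates are:

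- **The highest of that period's three pre-dose values.** It needs no outside figure, and is right in about 70–75% of profiles under the noise model.
- **A corrected value above 5% of Cmax.** Section 9.1.3 already uses this threshold. It did better on the fed profile, but its absolute level moves with Cmax and so can differ between treatments.

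State as well whether corrected values below the LLOQ are set to 0.

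The cost is a sentence or two, with no new samples or assays. The downside is that a slow initial rise may be detected one sample later.

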9.3 Pharmacokinetic Statistical Analysis

Statistical analysis described in this section will be based on the PK statistical population.

Individual and mean plasma concentration versus time curves will be presented for both linear and semi-log scales.

Descriptive statistics for the PK parameters of baseline-corrected and uncorrected sapropterin will be calculated. Descriptive statistics will include number of observations, arithmetic mean, standard deviation, geometric mean (where applicable), coefficient of variation (CV), median, minimum, and maximum.

Statistical analysis will be performed on quality assured data, with unbalanced sequences if necessary, from subjects in the statistical dataset. The PROC MIXED procedure from SAS® (version 9.4 or later) will be used.

ANOVA will be performed on log-transformed AUC_{0-t} , $AUC_{0-\infty}$, and C_{max} parameters at the alpha level of 0.05 on uncorrelated data, the statistical model will include sequence, treatment, period, and subject(sequence) as a random effect.

ANCOVA (Analysis of Co-Variance) on log-transformed AUC_{0-t} , $AUC_{0-\infty}$, and C_{max} parameters at the alpha level of 0.05 will be applied for baseline corrected analysis, using the actual total dose included in the ANOVA statistical model as a covariate, the statistical model will include sequence, treatment, period, and actual total dose as fixed effects and subject(sequence) as a random effect.

In case the study is dosed in groups, considering the study conduct will occur at the same clinical site, assignment to groups is random, and the dosing of the groups will occur within a relatively short timeframe, it is not anticipated that dosing in groups will impact the study results. As such, the group effect will not be considered in the statistical model.

Using the same statistical model, the least-squares-means, the differences between the treatments least-squares-means, and the corresponding standard errors of these differences will be estimated for log-transformed AUC_{0-t} , $AUC_{0-\infty}$, and C_{max} parameters. Based on these statistics, the ratios of the geometric means for treatments and the corresponding 90% confidence interval will be calculated for the following comparisons:

- Treatment A versus Treatment D
- Treatment B versus Treatment D
- Treatment C versus Treatment D
- Treatment B versus Treatment C
- Treatment A versus Treatment C
- Treatment B versus Treatment A

These contrasts will be estimated separately using only the data from the treatments involved in the comparison.

Treatment differences in T_{max} will be evaluated by a nonparametric approach (Wilcoxon signed rank test) on the untransformed values.

These statistics will be used to evaluate the effect of food on the test formulation and the performance of the test formulation with and without water.

Additional PK statistical analysis may be performed. For example, an analysis with potency corrected data (to adjust the ratio and 90% CI for the comparison between Test and Reference B/D), in the event that the measured study treatment content of the lots of the Test and Reference products would differ by more than 5%.

9.4 Safety and Tolerability Analysis

Demographic parameters will be summarized descriptively.

Safety and tolerability analysis will be performed for all subjects in the safety population. No inferential statistical analysis of safety data is planned.

Safety and tolerability of sapropterin dihydrochloride will be evaluated through the assessment of AEs (i.e., seriousness, severity, relationship to the study treatment, outcome, duration, and management), vital signs, 12-lead ECGs, clinical laboratory tests, and physical examinations. AEs will be coded using the latest version of the Medical Dictionary for Regulatory Activities (MedDRA).

TEAEs will be tabulated by treatment. Safety and tolerability data will be reported using descriptive statistics.

10. Data Collection

The source data will be collected on paper as per site SOPs. Source data will reflect the ALCOA+ principles, then they should be attributable, legible, contemporaneous, original, accurate, and complete. Source documents will be maintained in order to maintain data integrity. The Investigator and/or the clinical staff have the responsibility of ensuring the accuracy, completeness, legibility, and timeliness of the source data.

Details on the data management process will be described in a data management plan (DMP).

11. Regulatory Considerations and Quality Assurance

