Day	-30 to -1 (of Period 1)	-1 of Period 1 or prior to Period 1 dosing	-1 of Period 2, 3, 4	1	2 EOS/ET¹³
Screening consent ¹	X				
Informed consent ²		X			
Inclusion/exclusion criteria	X ³	X ⁴			
Demographic data	X ³				
Medical and medication history	X ³	X	X		
Confinement ⁵		X	X	X	
Discharge					X
Study treatment administration					
Sapropterin dihydrochloride oral suspension				X ⁶	
Kuvan powder for oral solution				X ⁶	
Pharmacokinetics					
Blood samples for PK analysis ⁷				X	X
Safety					
Physical examination ⁸		X			X
Body measurements (height, weight, BMI)	X ³	X ⁹			
Vital signs ¹⁰	X ³	X	X	X	X
12-lead ECG ¹¹	X ³			X	X
Serology tests	X ³				
Biochemistry, hematology, and urinalysis tests	X ³				X
FSH/LH (for post- menopausal females)	X ³				
Serum pregnancy tests	X ³	X	X		X
Urine pregnancy test		X	X		
Urine drugs of abuse	X ³	X	X		
Breath alcohol		X	X		
Monitoring and recording of AEs and prior/concomitant medication use		X	X	X	X

Abbreviations: AE = adverse event; BMI = body mass index; ECG = electrocardiogram; EOS = end of study; ET = early termination; FSH = follicle-stimulating hormone; LH = luteinizing hormone; PK = pharmacokinetic.

1 Includes privacy and volunteer consent. During screening, subjects will consent to and sign privacy and volunteer consent forms.

2 An informed consent form (ICF) specific to this study will be signed by all subjects at Period 1 check-in (Day -1), and before any study specific procedure.

- 3 Screening procedures can be done either at the screening visit or at Period 1 check-in (or repeated at both screening visit and Period 1 check-in if deemed necessary by the Investigator).
- 4 Complete outstanding procedures for inclusion/exclusion criteria confirmation.
- 5 Confinement period is at least 10.5 hours pre-dose until 24 hours post-dose.
- 6 On Day 1 of each period, subjects will receive one of the four treatments, according to the randomization scheme.
- 7 A total of 20 blood samples will be collected for PK analysis in each period: -1, -0.5, pre-dose (0-hour), and 0.333, 0.667, 1, 1.5, 2, 2.5, 3, 3.5, 4, 4.5, 5, 5.5, 6, 8, 12, 16, and 24 hours post-dose.
- 8 A complete physical examination will be performed at Period 1 check-in. A brief physical examination will be performed at EOS. Refer to sections 8.1 and 8.4 for more details.
- 9 Weight only at check-in of Period 1.

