- 10 Blood pressure, pulse rate, respiration rate, and temperature will be measured at screening and EOS. Temperature will be measured daily during confinement. Blood pressure and pulse rate will be measured before dosing (0-hour) and at 4 and 6 hours post-dose of each period.
- 11 12-lead ECG will be measured at screening, before dosing (0-hour), at 4 and 6 hours post-dose of each period, and at EOS.
- 12 There are 4 treatment periods. There will be a washout period of at least 7 days between doses.
- 13 EOS evaluations will be performed prior to study discharge of the last period. In case of ET, EOS procedures will be performed as soon as possible.

1. Introduction

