8.2 Test/ Procedures at check-in

Check-in of Period 1

- ICF signature for the study (if not done before);
- Medical and medication history;
- Any outstanding screening procedure that is not completed, or needs to be repeated;
- Complete physical examination including assessments of the following: head, eyes, ears, nose, throat (HEENT), neck, chest, lungs, abdomen, musculoskeletal, dermatological, cardiovascular/peripheral vascular, and general neurological examination;
- Temperature measurement;

- Weight;
- Urine drugs of abuse (amphetamines, barbiturates, benzodiazepines, cannabinoids, cocaine, methadone, opiates, phencyclidine, and tricyclic antidepressants);
- Urine β -HCG and serum β -HCG (females only);
- Breath alcohol;
- Confirm inclusion/exclusion criteria.

Check-in of Period 2, 3, 4

- Temperature measurement;
- Urine drugs of abuse (amphetamines, barbiturates, benzodiazepines, cannabinoids, cocaine, methadone, opiates, phencyclidine, and tricyclic antidepressants);
- Urine β -HCG and serum β -HCG (females only);
- Breath alcohol;
- Medical and medication history.

Clinical study personnel reserve the right to conduct additional testing (e.g., breath alcohol test, diagnostic imaging) at any time throughout the study.

8.3 On-study procedures:

- Temperature measurement daily;
- Vital signs (blood pressure and pulse rate) will be measured after the subjects have been resting for at least 3 minutes in a sitting position: before dosing (0-hour), and at 4 and 6 hours post-dose;
- 12-lead ECG will be recorded after the subjects have been resting in a semi-recumbent or supine position: before dosing (0-hour), at 4 and 6 hours post-dose;
- Study treatment administration; and
- Pharmacokinetic Blood Sample Collection: -1, -0.5, pre-dose (0), and 0.333, 0.667, 1, 1.5, 2, 2.5, 3, 3.5, 4, 4.5, 5, 5.5, 6, 8, 12, 16, and 24 hours post-dose.

Table 8. Time Windows for PK Blood Samples

Day	Time point	Time window
1	-1 hour, and -0.5 hour	± 5 minutes
	Pre-dose (0-hour)	Within 5 minutes
	0.333, 0.667, 1, 1.5, 2, 2.5, 3, 3.5, 4, 4.5, 5, 5.5, and 6 hours	± 1 minute
	8, 12, and 16 hours	± 3 minutes

2	24 hours	±3 minutes
---	----------	------------

Samples collected outside the acceptable window will not be considered as protocol deviations, but rather the actual clock time of each sample collection will be recorded.

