8.7 Adverse Events

8.7.1 Definition of Adverse Event

An AE is defined as any untoward medical occurrence in a patient or clinical trial subject administered a pharmaceutical product and which does not necessarily have a causal relationship with the treatment. An AE can, therefore, be any unfavorable and unintended sign (including an abnormal laboratory finding, for example), symptom, or disease temporally associated with the use of a medicinal (investigational) product, whether or not considered related to the medicinal (investigational) product.

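### Laboratory tests and physical examinations are scheduled only before the first dose and at end of study, so abnormalities first found at end of study cannot be assigned to a treatment in the by-treatment TEAE table

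*Combined protocol and SAP*

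**What the plan says.** Section 9.4 (and the Synopsis) states that "TEAEs will be tabulated by treatment". It names clinical laboratory tests and physical examinations among the safety assessments, reports safety descriptively, and plans no inferential safety analysis.

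In Table 1 the row "Biochemistry, hematology, and urinalysis tests" is marked only under screening and under the Day 2 EOS/ET column. Footnote 13 says that "EOS evaluations will be performed prior to study discharge of the last period" and that "In case of ET, EOS procedures will be performed as soon as possible". Footnote 3 adds that "Screening procedures can be done either at the screening visit or at Period 1 check-in". Footnote 8 places a complete physical examination at Period 1 check-in and a brief one at EOS. The check-in list for Periods 2 to 4 (section 8.2) and the on-study list (section 8.3) include neither routine safety laboratory tests nor a physical examination. Section 8.2 does note that "Clinical study personnel reserve the right to conduct additional testing".

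Section 8.7.1 counts as an AE "any unfavorable and unintended sign (including an abnormal laboratory finding, for example), symptom, or disease temporally associated" with use of the product. The visible text does not define a TEAE, say how an event is assigned to one of the four crossover treatments, or give a denominator for the by-treatment table.

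**The concern.** By the EOS sample, a subject who completes the study has received A, B, C and D. One post-treatment sample set against one pre-treatment sample shows that something changed, but not after which dose. Vital signs and ECGs are different: they are taken before dosing and at 4 and 6 hours in every period, so a finding can be placed within a treatment.

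Tabulating every TEAE by treatment therefore produces per-treatment rates for laboratory and physical examination findings that the schedule cannot support. Even a purely descriptive table with columns for A, B, C and D will be read as a comparison of Test with Reference. A real difference could be diluted or smeared in it without any sign to the reader.

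**Working it through.** The plan gives no laboratory TEAE rate to reproduce. The check counts what the schedule can observe, then asks what a by-treatment table would show under a stated rule.

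**Inputs from the protocol**
- 16 subjects planned (section 5.1).
- Four sequences (Table 3): DCAB ends in B, ADBC in C, BACD in D, CBDA in A.
- Washout of at least 7 days; EOS assessments before discharge from the last period.

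**Assumptions, not in the protocol**
- Equal split: 16 / 4 = 4 subjects per sequence, all completing four periods.
- An EOS finding is assigned to the most recent treatment.
- The denominator is all 16 subjects dosed with the treatment.
- p is the true risk of a laboratory abnormality on a treatment, and q is the chance that an abnormality lasts through one washout. Both are illustrative.

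**Coverage.** Each treatment is last in exactly one sequence, so it has scheduled post-dose laboratory tests as the last treatment in 4 of 16 subjects (25%). Under these assumptions no treatment can show an EOS laboratory rate above 25%.

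**Formula.** For a sequence with risks p1 to p4 in period order:

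P(abnormal at EOS) = 1 − (1 − p1·q³)(1 − p2·q²)(1 − p3·q)(1 − p4)

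Tabulated rate for the last treatment = (4/16) × P.

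**Transient changes (q = 0).** P = p4, so the tabulated rate is p/4. A true 10% shows as 2.5% for every treatment.

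**Changes that can outlast the washout.** Take true risks of 20% for A and 5% for B, C and D:

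| q | A | B | C | D |
|---|---|---|---|---|
| 0 | 5.0% | 1.25% | 1.25% | 1.25% |
| 0.25 | 5.3% | 2.5% | 1.7% | 1.9% |
| 0.5 | 5.9% | 4.0% | 2.7% | 3.1% |
| 1 | 7.85% | 7.85% | 7.85% | 7.85% |

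Example for A at q = 0.5 (sequence CBDA): 1 − 0.99375 × 0.9875 × 0.975 × 0.8 = 0.2346, and 0.2346 / 4 = 5.9%. At q = 1: 1 − 0.8 × 0.95³ = 0.3141, and 0.3141 / 4 = 7.85% for every treatment. The true fourfold difference is kept at q = 0, shrinks as q rises, and is gone at q = 1.

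**Alternative denominator.** Using only the 4 subjects for whom the treatment came last, a true 10% risk on every treatment shows as 10% at q = 0, 12.9% at q = 0.25, 17.7% at q = 0.5 and 34.4% at q = 1. This is unbiased only if nothing persists past the washout, and it rests on 4 subjects per treatment.

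**Distance from baseline.** At the minimum washout the fourth dose falls on Day 1 + 3 × 7 = Day 22 and EOS on Day 23. With no Day 0, the baseline laboratory sample precedes EOS by up to 30 + 23 − 1 = 52 days. If it was drawn on Day -1, the gap is 1 + 23 − 1 = 23 days.

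**The case against.** A reader might infer that laboratory TEAEs are credited to whichever treatment came last, that three quarters of them therefore go to the wrong treatment, and that 12 of 16 persistent changes caused by Reference would be booked to Test. The documents do not support this. No section states a last-treatment rule or a denominator of 16. The three-quarters figure also needs a change that survives at least one washout of 7 days or more. The mean half-lives in Table 2 are 2.80 to 4.65 h, so 168 h is at least 168 / 4.65 ≈ 36 half-lives. An effect can outlast the drug, but the protocol gives no reason to expect it here.

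If changes are transient, an EOS sample about 24 hours after the Period 4 dose reflects the Period 4 treatment, and assigning it there is correct. The dilution is then the same for all four treatments under balanced sequences, so no product is favored and ratios between treatments are preserved. Early-termination samples may follow a single treatment, in which case attribution is clear. Unscheduled and repeat tests are allowed. Safety is descriptive, the study is exploratory, and every treatment gives the same active ingredient at the same nominal 10 mg/kg.

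All of this stands, and it limits the size of the point. The core remains. Whether a given EOS abnormality is transient or persistent cannot be told from one post-dose sample. No per-period laboratory test is planned. The causality grading in section 8.7.4 rates the relationship to study treatment, not which of several administrations was responsible.

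**Conclusion.** The point holds as a limited one. For subjects who have received more than one treatment, AEs first detected by EOS laboratory tests or EOS physical examination cannot be validly assigned to a treatment from the planned data, yet section 9.4 tabulates all TEAEs by treatment.

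The size depends on the rule applied. With last-treatment assignment and all dosed subjects as denominator, coverage is about 4 of 16 per treatment, transient changes show at about one quarter of their true rate, and persistent changes are blurred across treatments. These figures assume balanced sequences and full completion. The p and q values are illustrations, not estimates.

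It does not follow that the laboratory rates will be wrong in favor of one product, or that most findings will be misassigned. The consequence is confined to descriptive safety tables, and the PK endpoints are untouched. The change is worth making because it is cheap.

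**What to change.** Add one paragraph to section 9.4:
- Report AEs first detected by EOS-only assessments (laboratory tests and physical examination) separately, over all treatments combined.
- Support them with a listing that gives treatment sequence, last treatment received and days since each dose.
- Keep by-treatment tabulation for events observed in every period (symptoms, vital signs, ECGs), and for early-termination subjects who received only one treatment.

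The cost is a paragraph and one extra table or listing, with no new procedure, sample or visit. The downside is that no per-treatment rate is shown for EOS-detected laboratory AEs, but the present schedule cannot supply a dependable one.
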